11.4. Reporting procedures

Together with the UW ICTR Data Monitoring Committee (DMC) we will develop a detailed a data and safety monitoring plan (DSMP) which will ensure ongoing safety of participating patients commensurate with the level of risk and complexity of the protocol treatment to minimize risks, integrity of trial data and scientific validity of the trial. The development of the DSMP will be guided by the NIH Policy for Data and Safety Monitoring and by the FDA Guidance on the Establishment and Operation of Clinical Trial Data Monitoring Committees. The plan will make certain that review of the conduct of research is rigorous, independent and objective, interim safety and efficacy data is collected and presented, and progress towards achieving study goals is made. It will cover policies and procedures for reporting adverse events to the DMC, IRB, and the drug manufacturer(s).

11.4.1. Adverse Event Reporting

Only the adverse events considered related (possibly, probably or definitely) to the ingestion of the study drug will be entered into and managed in the data management system and be made available to the study team for cumulative review, as well as the DMC and SMS.

Based on the subject population, it is anticipated that the laboratory results that will be abstracted from the EMR for study purposes will be abnormal. The PI will not make clinically significant/non-clinically significant determinations of these results, as this subject population is expected to be abnormal and clinically significant hence their current clinical treatment. All reportable events related to the study protocol and its associated procedures will be reported to the IRB. It is the responsibility of the Investigator to promptly notify the Institutional Review Board of all unanticipated problems involving risk to human research subjects. Reportable events, such as protocol noncompliance, serious adverse events, new information, and unanticipated problems will be reported to the IRB and DMC in accordance with the UW IRB guidelines.

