10.2.5. Data Collection Tools

Online Collaborative Research Environment (OnCore) will serve as the Clinical Trial Management System for this study. ICTR OnCore is supported by the UW School of Medicine and Public Health Information Technology (SMPH-IT) staff and managed by UW ICTR.

OnCore is a sophisticated, web-based data management system that: a) ensures secure, easy data entry at multiple sites; b) integrates multiple data sources; c) provides controlled, secure access to sensitive data using role-based access control; d) provides workflow automation; and e) allows export and reporting of data for Data and Safety Monitoring Boards and biostatisticians. This software provides protocol management functions (e.g. subject scheduling; screening, data organization), maintains updated forms, addresses budget development, billing, and fiscal management, generates summary reports, and provides essential links with other research administration and electronic medical records systems. ICTR OnCore eases the burden of the individual researcher and unifies protocol management within research programs and across research sites, enhancing protocol integrity and regulatory compliance efforts.

Data extracted from the EMR will be entered into the REDCap system managed by ICTR. This data will be combined with the data exported from the OnCore system and imported into the same project, allowing REDCap to serve as the final data repository for this study.

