10.4. Records Retention

Study records will be retained for a minimum of 7 years after study completion per the UW Madison policy and IRB guidance: <https://kb.wisc.edu/sbsedirbs/page.php?id=42378>. These documents should be retained for a longer period if required by an agreement with the sponsor. In such an instance, it is the responsibility of the sponsor to inform the investigator/institution as to when these documents no longer need to be retained.

11. Assessment of Safety

The investigator is responsible for monitoring the safety of subjects who have enrolled in the study. For this study, adverse events will be solicited from subjects to identify an occurrence or worsening of an unintended sign or symptom,

related to the ingestion of the study drug as per standard of care. The clinical team will ask subjects in each visit if they experienced any new medical related signs or symptoms since taking the study drug. Subjects will be asked about any adverse events they may have experienced. Only the adverse events considered related (possibly, probably or definitely) to the ingestion of the study drug will be entered into and managed in the data management system.

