11.3. Time period and frequency for event assessment and follow-up

The occurrence of an AE or SAE may come to the attention of study personnel during study visits and interviews of a study participant presenting for medical care, or upon review by a study monitor. All AEs including local and systemic reactions not meeting the criteria for SAEs will be captured on the appropriate CRF. Information to be collected includes event description, time of onset, clinician's assessment of severity, relationship to study product (assessed only by those with the training and authority to make a diagnosis), and time of resolution/stabilization of the event. All AEs occurring while on study must be documented appropriately regardless of relationship. All AEs will be followed to adequate resolution.

Any medical condition that is present at the time that the participant is screened will be considered as baseline and not reported as an AE. However, if the study participant's condition deteriorates at any time during the study, it will be recorded as an AE. UPs will be recorded in the data collection system throughout the study.

Changes in the severity of an AE will be documented to allow an assessment of the duration of the event at each level of severity to be performed. AEs characterized as intermittent require documentation of onset and duration of each episode.

The PI will record all reportable events with start dates occurring any time after the administration of the study drug and for up to 30 days after the date of the last dose of study drug. At each study visit, the investigator will inquire about the occurrence of AE/SAEs since the last visit. Events will be followed for outcome information until resolution, stabilization, or completion of study participation.

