11.4.4. Events of special interest

The safety data that will be reviewed includes the number and seriousness of infections, malignancies, hematological complications including leucopenia, anemia, and thrombocytopenia, cardiovascular complications and events, neurological symptoms, gastrointestinal symptoms, and immunosuppression-related adverse effects

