12.1. Medical Monitoring

The investigator is responsible for monitoring the safety of subjects who have enrolled in the study. For this study, adverse events will be solicited from subjects to identify an occurrence or worsening of an unintended sign or symptom, related to the ingestion of the study drug. The study team will ask subjects on each evaluation if they experienced any new medication related signs or symptoms since taking the study drug. Subjects will be asked about any adverse events they may have experienced on each visit. Only the adverse events considered related (possible, probable or definite) to the ingestion of the study drug will be entered into and managed in the data management system.

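### Adverse events enter the database only if an unblinded clinician judges them related to the study drug, against Section 11.3, so recorded non-serious AE rates may differ between arms through attribution alone

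*Combined protocol and SAP*

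**What the plan says.** **The filter.** Four places make relatedness a condition for entry in the study database. Section 11.4.1: "Only the adverse events considered related (possibly, probably or definitely) to the ingestion of the study drug will be entered into and managed". The opening of Section 11 and Section 11.1.1 use the same words ("Only the adverse events considered related (possibly, probably or definitely) to the ingestion of the study drug"), and 12.1 is almost identical ("Only the adverse events considered related (possible, probable or definite) to the ingestion of the study drug"). Section 11.4.1 adds that the filtered entries will "be made available to the study team for cumulative review, as well as the DMC and SMS".

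**The opposing rule.** Section 11.3: "All AEs including local and systemic reactions not meeting the criteria for SAEs will be captured on the appropriate CRF". It continues: "All AEs occurring while on study must be documented appropriately regardless of relationship". The CRF is to hold severity, relationship, onset and resolution.

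**The safety events of interest.** Section 5.1.3 lists the primary safety endpoints and 11.4.4 lists what will be examined ("The safety data that will be reviewed includes the number and seriousness of infections", followed by further event types). Neither mentions relatedness.

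**The data path.** Section 10.2.2 describes paper CRFs and 10.2.3 direct electronic entry. Section 10.2.5 combines the EMR extract with the OnCore export, "allowing REDCap to serve as the final data repository for this study". Under 11.6, the DMC's reports are built from OnCore and REDCap.

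**Who judges, and about what.** The trial is unblinded (7.4) and the examining clinician decides causality (11.2.2). The term study drug is attached to Envarsus XR in the Study Summary, 6.7.2 and 6.7.3. Section 7, headed Study Agent, lists both arms, and exclusion criterion 1 uses the plural.

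**The concern.** Both arms receive tacrolimus, so the informative safety result is the comparison of the 5.1.3 events between formulations. If an event counts only after a clinician who knows the arm has called it related, the recorded rate is the product of the true rate and the attribution habit in that arm. A newer formulation may draw more suspicion than a familiar one, or less. The uncertain scope of the term study drug in the control arm adds a second way for the arms to be handled differently. A difference in recorded rates could then be created or hidden without any difference in true rates. The oversight committee would be looking at the same filtered data.

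**Working it through.** **Step 1. Can the passages be reconciled?** The natural attempt is two tiers: all AEs on CRFs and source documents (11.3), only related ones in the electronic system (11, 11.1.1, 11.4.1, 12.1). This removes the literal clash but not the consequence:

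- Section 11.4.1 ties what the study team, DMC and monitors receive to the filtered entries.
- Section 10.2.5 makes REDCap the final dataset.
- Section 11.6 draws DMC reports from OnCore and REDCap.

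Non-serious events judged unrelated therefore drop out of system-based review. They also drop out of the analysis data, unless the review of medical records and the Transplant Database for endpoints and safety in the study schematic (Section 1, Figure 1) brings them in. The plan does not say what that review enters.

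**Step 2. What is outside the problem.** SAEs go to the DMC on the SAE Form (11.4.2), although entry of unrelated SAEs in the database is not stated. Laboratory values are entered directly (10.2.3). The efficacy endpoints do not pass through the filter.

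**Step 3. Illustration of size.** The plan gives no AE or attribution rate, so there is no figure of its own to reproduce.

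- From the plan: n = 50 per arm (9.1); Fisher's exact test as one of two generic options for categorical data, and p < 0.05 (9.2).
- Assumed: a two-sided test; true risk p; attributed share r in each arm.

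Recorded rate: q = p × r. The chance of a significant result is the sum over all pairs (i, j) of Bin(i; 50, q1) × Bin(j; 50, q2), counting only pairs whose Fisher p-value is below 0.05.

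No true difference between arms:

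| Attribution | p = 20%: q1 vs q2, chance | p = 40%: q1 vs q2, chance | p = 60%: q1 vs q2, chance |
|---|---|---|---|
| 60% vs 30% | 12% vs 6%, 9% | 24% vs 12%, 26% | 36% vs 18%, 45% |
| 80% vs 60% | 16% vs 12%, 5% | 32% vs 24%, 10% | 48% vs 36%, 18% |
| 90% vs 80% | 18% vs 16%, 3% | 36% vs 32%, 5% | 54% vs 48%, 7% |
| all entered | 20% vs 20%, 3% | 40% vs 40%, 3% | 60% vs 60%, 3% |

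True difference 50% vs 25%:

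| Case | Recorded rates | Power |
|---|---|---|
| All entered | 50% vs 25% | 67% |
| Equal attribution 90%, independent of cause | 45% vs 22.5% | 59% |
| Equal attribution 80%, independent of cause | 40% vs 20% | 52% |
| 80% in the higher-risk arm, 90% in the lower | 40% vs 22.5% | 39% |
| 90% in the higher-risk arm, 80% in the lower | 45% vs 20% | 71% |
| Half of the 25% background dropped in both arms, excess kept | 37.5% vs 12.5% | 79% |

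In the last row 12.5 points are removed from each arm: 50 − 12.5 = 37.5 and 25 − 12.5 = 12.5.

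**The case against.** The case for leaving the text alone has real content.

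- **The filter looks deliberate.** It is stated four times and can coexist with full capture on paper. This stands as a reading, but step 1 shows that review and analysis still see only the filtered events.
- **Attribution may be high and similar.** Section 11.2.2 says the product is always to be suspected and asks only for some evidence, such as timing, for a possible relation. Section 3.5.1 describes the risks of the two formulations as nearly alike. At 90% vs 80% the false-positive chance is 3% to 7%. This stands: the effect may be small.
- **No between-arm AE test is specified.** Section 9.2 is generic and 9.3 names only dose adjustment and DGF recovery. This stands; the comparison is implied by 5.1.3.
- **The DSMP may settle what the DMC receives.** Sections 3.5.2 and 11.4 assign AE reporting procedures to it, and its text is not available here. It could help, but the protocol would still contradict itself.
- **Filtering can help.** If only background noise is removed, power rises (79% against 67%). This stands, so a loss of power under equal attribution is conditional.

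A reader might also infer that control-arm events can never qualify, because study drug means Envarsus XR in three places. With an assumed 50% attribution in the Envarsus XR arm and none in the control arm, a 40% true risk would give recorded rates of 20% vs 0% and a 95% chance of significance. The documents do not support that reading firmly: causality is graded against the study agent, and Section 7 lists both arms under that heading.

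**Conclusion.** The conflict between 11.3 and the four filter statements is explicit and should be resolved. The conflict with 5.1.3 and 11.4.4 is by implication only, since those sections are silent on relatedness. The consequence is limited to non-serious clinician-reported AEs judged unrelated: they are not made available through the system to the study team, DMC or monitors, and are absent from REDCap unless the unspecified chart review captures them.

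Recorded rates may therefore differ between arms through attribution alone. Size and direction are unknown. The range of 3% to 45% across the unequal-attribution cases with no true difference rests wholly on assumed attribution and risk. Equal attribution adds no bias when there is no true difference. It lowers power if attribution is independent of true cause, and can raise it otherwise.

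Three stronger conclusions are tempting and not supported:

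- That differential attribution could never be detected: 11.3 puts relationship on the CRF for every AE, so the split by arm could be recovered from there.
- That these events are certainly missing from REDCap: the chart-review route is open.
- That SAEs are wholly untouched: they reach the DMC, but database entry of unrelated ones is not stated.

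This should be fixed. It does not threaten the efficacy endpoints.

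**What to change.** Reconcile Section 11, 11.1.1, 11.4.1 and 12.1 with 11.3 by one rule: all AEs, including SAEs, in both arms are entered in the data management system, and relatedness to the assigned tacrolimus formulation is recorded as a variable and is not a condition for entry. Define the term study drug once for this purpose, so that its scope in the control arm is clear. Report all-cause rates of the 5.1.3 endpoints by arm, with related-only rates as a secondary display.

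The cost is extra data entry for events that 11.3 already requires on the CRF with their relationship. No new visit or test is needed. Related-only tables, where these are preferred, remain available from the same data.

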5.1.3. Primary Safety Endpoints

Primary safety endpoints include: infections, malignancies, hematological complications including leukopenia, anemia, and thrombocytopenia, cardiovascular complications and events, neuropathy, tremors, gastrointestinal symptoms, uncontrolled hypertension, serious electrolytes abnormalities and immunosuppression-related adverse effects.

6. Study Subjects – Enrollment and Withdrawal

- A total of 100 subjects (50 subjects in each arm) with the diagnosis of DGF will be enrolled over a period of 2 years.
- DGF is defined as the need for a dialysis within the first week of transplant. Once potential DGF patients are identified, the transplant nephrology team will be consulted and the transplant nephrology provider will perform initial evaluation of a patient, discussion with the patient about his/her interest in participating in the research study and inform the research coordinator.
- Subjects will participate in the study until the recovery of DGF as documented by the provider as “discharged from the DGF clinic” or no need for dialysis for more than one week (7 days).
- Subject would be followed for maximum of 3 months. If they still need dialysis beyond 3 months, will be declared as primary dysfunction and will disqualify from the study.

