10.2.3. Electronic Case Report Forms (eCRFs)

Some of the data that will be exported for analysis will not be captured on paper CRFs, rather directly entered into the ICTR OnCore or ICTR REDCap Data Management System, including but not limited to results of laboratory tests, physical examinations, imaging, etc.

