11.1.1. Definition of Adverse Events (AE)

Adverse event (AE) means any untoward medical occurrence in a patient or subject administered a pharmaceutical product; the untoward medical occurrence does not necessarily have a causal relationship with this treatment. An AE can therefore be any unfavorable and unintended sign, symptom, or disease temporally associated with the use of a medicinal (investigational) product whether or not it is related to the medicinal product. This includes any newly occurring event, or a previous condition that has increased in severity or frequency since the administration of study drug. AEs will be assessed at study visits and during the final follow-up study visit. Only the adverse events considered related (possibly, probably or definitely) to the ingestion of the study drug will be entered into and managed in the data management system

For the purposes of this study, baseline symptoms will be collected prior to the administration of study intervention. Only those symptoms identified as new or worsened compared to the baseline assessment will be recorded as an AE. In addition, only those abnormal laboratory values or physical examination assessments that are considered clinically significant will be recorded in the study documents. [Pain and hematoma at transplant incision site will not be considered an AE.](#)

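### The plan does not settle who decides, or by what threshold, when an abnormal laboratory value becomes a recorded event, so adverse-event counts for four primary safety endpoints are not reproducible

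*Combined protocol and SAP*

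**What the plan says.** Section 5.1.3 (Primary Safety Endpoints) names "hematological complications including leukopenia, anemia, and thrombocytopenia" and, later in the same list, "serious electrolytes abnormalities and immunosuppression-related adverse effects". It gives no laboratory cut-off for any of them and does not define what makes an electrolyte abnormality serious.

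Section 11.1.1 (Definition of Adverse Events) sets the recording rule: "only those abnormal laboratory values or physical examination assessments that are considered clinically significant will be recorded in the study documents". It does not say who does the considering.

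Section 11.4.1 (Adverse Event Reporting) anticipates that "the laboratory results that will be abstracted from the EMR for study purposes will be abnormal". It continues: "The PI will not make clinically significant/non-clinically significant determinations of these results", and gives as the reason "as this subject population is expected to be abnormal and clinically significant hence their current clinical treatment".

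Section 10.2.3 (Electronic Case Report Forms) describes some of the study data as "directly entered into the ICTR OnCore or ICTR REDCap Data Management System, including but not limited to results of laboratory tests". No significance filter is attached there.

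**The concern.** Leukopenia, anemia, thrombocytopenia and electrolyte disturbance are all read from blood tests. Whether a patient counts as having one depends on the step that turns a laboratory value into an event. Section 11.1.1 makes that step a judgement. Section 11.4.1 takes the judgement away from the one person it mentions and hands it to nobody else.

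At stake is the between-arm safety comparison on named primary safety endpoints. Section 3.5.1 lists hyperkalemia and electrolyte disturbance among the known risks of the study drug, and section 11.1 puts thrombocytopenia and neutropenia among the areas to be watched closely. If the rule for counting these events is open, a difference between arms, or the lack of one, may reflect recording practice and not toxicity.

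**Working it through.** The plan states no figure on this point, so the check is a comparison of the sections.

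**Step 1. Who judges, and against what?**
- 11.1.1: the value must be considered clinically significant; no assessor is named.
- 11.4.1: the PI does not make that determination for the abstracted results.
- 11.2.1 and 11.2.2: the clinician grades severity on CTCAE v4 and assigns causality. Both apply to something that is already an adverse event. Neither says that the clinician decides whether a laboratory value is one, or that CTCAE is applied to every value.
- 5.1.3: no thresholds.

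No section supplies the missing assessor or the missing cut-off.

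**Step 2. What counts does the text allow?** Three readings fit the words.

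| Reading | Basis | Recorded laboratory events |
|---|---|---|
| The PI is the gatekeeper and makes no determination | 11.1.1 with the bar in 11.4.1 | None |
| The reason given in 11.4.1 is itself a blanket finding of significance | 11.1.1 with the reason in 11.4.1 | Nearly all abnormal values |
| Some other clinician decides case by case | 11.1.1, by analogy with 11.2.1 and 11.2.2 | Whatever each clinician chooses |

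Under the second reading, section 11.3 removes conditions already present at screening, but it brings back any deterioration and states no degree of laboratory worsening. With 50 patients per arm (section 6), the same laboratory data could therefore give a count anywhere from 0 up to the number of patients in that arm with any abnormal value, which is at most 50.

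**Step 3. Can the choice differ by arm?** Section 7.4 says that the study is unblinded. Under the third reading the person deciding knows the treatment, so it can.

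**Step 4. Does another part of the plan fix the count?**
- Values in the database (10.2.3, 11.4.1): present, but no section derives an endpoint from them.
- Safety review (11.4.4) and DMC report (11.6): both are described by number and seriousness of complications or adverse events. The listed contents of the DMC report include no laboratory tabulation.
- Asking patients about signs and symptoms (opening of section 11, and 12.1): this would miss a laboratory abnormality that causes none.

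**Step 5. Is this the same as the relatedness problem?** No. Section 11.4.1 enters only related events, while 11.3 asks for documentation regardless of relationship. That is a separate conflict affecting the same endpoints, and it arises only after a value has become an event.

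**The case against.** A reader might infer something stronger: that a site following both rules would record no laboratory events at all, so that these endpoints would come out empty and a real signal could not reach the DMC. The documents do not support that, for five reasons.

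- The bar in 11.4.1 names only the PI. Another clinician who judges a value significant does not break it.
- The reason given in 11.4.1 can be read as treating these results as significant by default. That points to over-recording, not to zero.
- Section 11.3 records deterioration of a condition as an adverse event and does not repeat the significance test.
- Laboratory results are abstracted and entered as data. Section 11.6 has statisticians build the DMC reports from both databases, section 12.1.1 has the DMC statistician take part in periodic central data reviews, and section 11.4.4 separately lists hematological complications for review. Serious events also reach the DMC through SAE reporting (11.4.2, 11.6).
- The DMC Charter and the Data and Safety Monitoring Plan are appendices whose text is not supplied here. They may describe laboratory displays.

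All of this stands against the stronger reading. It does not supply the missing rule. The values could be used, but the plan does not say that they will be or how. Other clinicians may record events, but by no common criterion. Whatever the appendices contain, 11.1.1 and 11.4.1 still disagree within the protocol.

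It is also fair to say that naming an assessor would remove the contradiction by itself. It would leave the endpoint resting on unblinded judgement.

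**Conclusion.** The point holds as one about reproducibility and possible bias. Sections 11.1.1 and 11.4.1 conflict on whether anyone judges clinical significance, and 5.1.3 gives no thresholds. The adverse-event counts for four laboratory-based primary safety endpoints can therefore be none, nearly all, or a matter of individual unblinded choice.

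The size cannot be given as a number. The documents state no expected rates for these events, and any bias depends on which reading the site adopts and whether it does so equally in both arms. The primary and secondary efficacy endpoints (5.1.1, 5.1.2) are not touched.

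The conclusion assumes that the unseen appendices do not already define these endpoints from laboratory values. If they do, the remaining defect is the contradiction in the protocol text.

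**What to change.** Reconcile 11.1.1, 11.4.1 and 10.2.3 so that they say the same thing about what happens to an abnormal laboratory value. Then state in 5.1.3 and section 9 that the laboratory safety endpoints are derived, identically in both arms, from the abstracted values and not from a clinical-significance judgement:

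- Grade each value on CTCAE v4, the scale already named in 11.2.1.
- Count a patient as having the event when the grade worsens from the last value before randomisation to a grade fixed in advance. Measuring change from baseline meets the valid concern in 11.4.1 that this population starts out abnormal.
- Tabulate the shift from baseline to worst grade by arm, and add the table to the DMC report in 11.6.
- Limit this to analytes actually abstracted. Section 8.1 lists CBC, BMP, magnesium, phosphorus and calcium as commonly obtained. Use neutrophils only where a differential exists, and otherwise the white cell count.

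Patients leave the study on recovery (8.2.3), so time under observation may differ by arm. Show it beside the table.

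The cost is protocol wording and a little programming. Section 8.1 has similar blood tests drawn in both groups as standard of care, so no new tests are needed and patient care does not change. The drawback is that more laboratory events may be listed than under clinician judgement.
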